### **6.1.1. *Definition of Baseline and postbaseline Measures***

The treatment period starts after administration of the first dose of baricitinib at Visit 6 (Week 0) and ends on the date of the final visit in the treatment period or the early discontinuation visit.

#### **NNS/CANDLE, SAVI, AGS**

**Baseline of the baricitinib treatment period** which includes dose adjustment period, primary treatment period and maintenance treatment period will be defined as the last available value before the first dose of baricitinib. In most cases, this will be the measure recorded at Week 0 (Visit 6). Change from baseline will be calculated as the visit value of interest minus the baseline value.

**Endpoint of the baricitinib treatment period** will be the last non-missing postbaseline measurement during the baricitinib treatment period. Major interest is the endpoint of the primary treatment period. Any measurements collected after the first dose of baricitinib will be considered a postbaseline measurement.

**Baseline of the post follow-up period** is defined as the date of the final visit or early termination in the treatment period. **Endpoint of the post follow-up period** is Visit 801.

#### **NNS/CANDLE (Comparison with pre-treatment period)**

In order to assess the change **from pre-treatment period** for NNS/CANDLE patients of efficacy measurements during baricitinib treatment period, average of all daily diary scores collected during pre-treatment period (i.e. from Visit 2 through Visit5) will be used as a baseline value.

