CANDLE typically presents clinically before 6 months of age with fever, repeated attacks of erythematous and violaceous, annular cutaneous plaques, persistent periorbital erythema and edema, finger or toe swelling, hepatomegaly, and variable elevation of acute-phase reactants. Another prominent clinical feature is progressive loss of peripheral fat (lipodystrophy). Patients fail to thrive and lymphadenopathy and hypochromic or normocytic anemia may be seen (Ramot et al. 2011; Torrelo et al. 2010).

In an international collaborative effort, 9 patients with the clinical diagnosis of CANDLE were studied (Liu et al. 2012). Genetic analyses showed that 7 out of 9 patients harbor a genetic mutation in PSMB8 of the immunoproteasome complex (i-proteasome). After the original report of CANDLE in 4 children, a syndrome diagnosed in 3 adult patients with joint contractures, muscle atrophy, microcytic anemia, and panniculitis-induced childhood-onset lipodystrophy was reported under the acronym “JMP” for joint contractures, muscle atrophy, and panniculitis (Garg et al. 2010). Patients with JMP were recently demonstrated to carry a PSMB8 mutation (Agarwal et al. 2010). Five patients were homozygous for the same mutation (T75M). Two patients were heterozygous for the T75M mutation, 1 patient was homozygous for a nonsense PSMB8 mutation (C135X), and 1 patient with clinical CANDLE was PSMB8-mutation negative, suggesting genetic heterogeneity and the possibility of other defects in the i-proteasome or the disease-associated pathway.

CANDLE patients have some overlapping features with JMP patients, including a cutaneous eruption and lipodystrophy (Garg et al. 2010). Although the patients reported as having JMP had more prominent joint contractures and muscle atrophy than patients described as having CANDLE, the detection of the same, and additional, mutations in PSMB8 unifies these disorders as proteasome-associated autoinflammatory syndromes (PRAAS). CANDLE patients present with recurrent febrile episodes, elevated acute-phase reactants, and a characteristic neutrophilic dermatosis with a mononuclear interstitial infiltrate including “immature” neutrophils in the dermis that seems pathognomonic for CANDLE (Torrelo et al. 2015). In fact, 2 patients have been misdiagnosed with acute cutaneous myelogenous leukemia.

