Concomitant therapy for primary diseases during the study is permitted as described in Section [7.7](#). Patients who have previously been treated with JAK inhibitors or biologic agents are eligible for the study. However, treatment must have been discontinued according to exclusion criterion #27 (Section [6.2](#)).

Investigators should review the vaccination status of their patients at screening. Immunization records will be collected in pediatric patients (<18 years of age). Immunization records for the BCG vaccine, varicella-zoster virus (VZV) vaccine, and herpes zoster (HZ) vaccine will be collected for all patients. Investigators ensure that patients are up to date with all immunizations, and follow the local requirements for vaccination guidelines and schedule for immunosuppressed

patients. No changes in start or resumptions of a vaccine is required, pediatric patients follow the Japanese immunization guidelines, with the exception of live vaccines.

All inclusion and exclusion criteria are provided in Sections [6.1](#) and [6.2](#), respectively. Patients with SAVI or AGS who meet all of the inclusion and none of the exclusion criteria will continue to Visit 6. Patients with NNS/CANDLE will continue to pre-treatment period after screening visit.

Pre-treatment Period (NNS/CANDLE only)

Pre-treatment period is 12 weeks period beginning at Visit 2 and natural history data with NNS/CANDLE patients will be collected through pre-treatment period. This applies only to NNS/CANDLE patients.

Patients who meet all of the inclusion and none of the exclusion criteria will continue to pre-treatment period. However, results of some tests (eg, laboratory tests) may not be available at Visit 2. In the case, patients will be performed procedures for pre-treatment period according to the Schedule of Activities (Section [2](#)). If a patient is identified not to meet enrollment criteria in accordance with screening test results, the patient should be discontinued from the study.

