### 6.1. General Considerations

Statistical analysis of this study will be the responsibility of Lilly or its designee.

Because the medical conditions being treated in this study are rare, it is anticipated that relatively few patients with each condition will be enrolled. Therefore, no formal statistical analyses are planned. Instead, descriptive summaries, where applicable, and data listings will be the main tools used to summarize the results from this study. When summary statistics are deemed appropriate, continuous data will be summarized in terms of the mean, standard deviation, minimum, maximum, median, and number of observations and categorical data will be summarized as frequency counts and percentages.

Any change to the data analysis methods described in the protocol will require an amendment only if it changes a principal feature of the protocol. Any other change to the data analysis methods described in the protocol, and the justification for making the change, will be described in the clinical study report (CSR). Additional exploratory analyses of the data will be conducted as deemed appropriate.

Patient's diary scores collected every day will be entered and stored into the clinical trial database and these data will be used for the efficacy analyses. Two types of derivations for the diary scores are planned; (1) "mean" daily diary scores and (2) proportion of days meeting threshold during treatment period. Details are described in Section 6.9.1.

- (1) **mean daily diary scores**; average scores from 7 days of preceding the current visit (not including data on the day of current visit) will be used as a representative value of the visit. If more than 50% symptom scores are missing for the specified calculation, then the average diary score will not be calculated.
- (2) **Proportion of days meeting threshold**; proportion of days which meets a threshold of response criteria for daily diary score will be used (e.g. daily diary score <0.5 for NNS/CANDLE). Given a interval (e.g. from previous visit to current visit, or during primary treatment period), the proportion of days will be calculated as total number of days meeting the threshold divided by total number of days with non-missing diary scores during the interval.

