## 6.8. Efficacy Analyses

### 6.8.1. Primary Outcome and Methodology

The primary objective is to determine if the administration of baricitinib to patients with NNS/CANDLE, SAVI, or AGS results in reduction in the patient's mean daily diary scores compared to baseline.

For change from baseline in patient's mean daily diary scores (defined in Section 6.9.1), descriptive statistics will be calculated by visit for NNS/CANDLE, SAVI, and AGS for baricitinib treatment period including dose adjustment period, primary treatment period and maintenance treatment period. Primary interest is to assess the mean change from baseline in patient's mean daily diary scores at Week 20 in NNS/CANDLE and Week32 in SAVI and AGS during primary treatment period, which is the primary endpoint of the study.

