#### 6.8.3.1. Comparison against pre-treatment period (NNS/CANDLE only)

In order to assess the change from pre-treatment period for NNS/CANDLE patients of efficacy measurements during baricitinib treatment period, the same analyses for the following primary and secondary efficacy variables will be performed by using average of data during pre-treatment period as a baseline value.

- Mean daily diary score
- Patient's symptom specific daily diary scores
- Proportion of days which meets a threshold of response criteria (See section 6.1)
- Physician's Global Assessment of Disease Activity scores

Proportion of days which meets a threshold of response criteria during both pre-treatment period and primary treatment period will be calculated.

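### NNS/CANDLE change from pretreatment sets a 7-day visit mean against a nominal 84-day average; adding a matched Week 8 to 20 period mean would make the individual result about half as noisy at little cost

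*SAP*

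**What the plan says.** SAP 6.1.1, under the NNS/CANDLE comparison with the pretreatment period, sets the baseline as the "average of all daily diary scores collected during pre-treatment period", running from Visit 2 through Visit 5. Protocol 5.1 gives the length: "Pre-treatment period is 12 weeks period beginning at Visit 2".

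SAP 6.8.3.1 says that the same analyses "will be performed by using average of data during pre-treatment period as a baseline value". They cover the mean daily diary score, the symptom scores, the proportion of days meeting the threshold and the physician's global assessment. The analyses referred to are by visit (SAP 6.8.1: "descriptive statistics will be calculated by visit for NNS/CANDLE, SAVI, and AGS for baricitinib treatment period"). SAP 6.1 defines the visit value of the diary score as "average scores from 7 days of preceding the current visit". SAP 6.1.1 fixes the arithmetic: "Change from baseline will be calculated as the visit value of interest minus the baseline value".

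One item is treated differently. SAP 6.8.3.1 states that the proportion of days meeting the threshold "during both pre-treatment period and primary treatment period will be calculated". Protocol 5.1 makes the NNS/CANDLE primary treatment period 12 weeks, Week 8 to Week 20, with the diary kept daily throughout the study.

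**The concern.** The pretreatment period was built to give each NNS/CANDLE patient a natural-history comparator. Protocol 3.2 describes a relapsing course ("CANDLE patients present with recurrent febrile episodes"), and Protocol 3.2.3 mentions flares with infection or stress. An 84-day average blends flare days and quiet days, whereas a 7-day mean may hold all of one kind. The difference between the two therefore depends partly on where the visit week falls in the flare cycle.

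About 5 patients are expected over three diseases, so NNS/CANDLE may contribute one to a few. Results will be read from listings and individual plots, and nothing averages out the luck of a single week. The daily scores needed for a like-for-like comparison are already in the database.

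**Working it through.** **Windows.** The plan has no power or sample-size calculation to reproduce. Its window lengths do reproduce. Visit 9 is Day 57 and Visit 12 is Day 141 in the Schedule of Activities, so 141 − 57 = 84 days = 12 weeks. Pretreatment starts at Day −84, also 12 weeks. The Week 20 value uses 7/84 = 8.3% of the primary-period diary. Visits 10, 11 and 12 together use 21/84 = 25%.

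**Hand example, no drug effect.** Let H be the flare-day score, L the quiet-day score, and f the share of flare days in a window. Then

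change = (H − L) × (f over 7 days − f over 84 days).

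Assume H = 1.5, L = 0.2 and a 7-day flare in every 28 days. None of these values is in the documents.

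- Pretreatment mean: (7 × 1.5 + 21 × 0.2)/28 = 14.7/28 = 0.525.
- Flare-free visit week: 0.2 − 0.525 = −0.325. This occurs at (28 − 7 − 6)/28 = 54% of positions in the cycle.
- Visit week wholly in flare: 1.5 − 0.525 = +0.975.
- 84 days against 84 days: three full cycles in each window, so the change is 0.

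**Simulation A, no drug effect.** 20,000 patients per row, random spells, H = 1.5, L = 0.2, daily noise SD 0.2.

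| Mean flare/quiet spell (days) | Flare-free visit week | SD, 7 vs 84 | SD, 84 vs 84 | Ratio | Apparent decrease, 7 vs 84 | Apparent decrease, 84 vs 84 |
|---|---|---|---|---|---|---|
| 5/23 | 63% | 0.41 | 0.20 | 2.0 | 67% | 50% |
| 7/21 | 56% | 0.48 | 0.26 | 1.9 | 64% | 50% |
| 10/18 | 46% | 0.57 | 0.32 | 1.8 | 58% | 50% |
| 14/14 | 32% | 0.60 | 0.35 | 1.7 | 50% | 50% |

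The mean change is 0.00 in every row under both methods. On average, flare-free weeks read as −0.23 to −0.64 and the other weeks as +0.29 to +0.40.

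**Simulation B, no drug effect.** H = 2.0, L = 0.2, flares of 5 to 7 days, mean cycle 21 to 42 days. The SD is 0.50 to 0.63 as planned and 0.21 to 0.27 with matched windows. The ratios are 0.54/0.22 = 2.5, 0.50/0.21 = 2.4, 0.63/0.27 = 2.3 and 0.56/0.24 = 2.3. A score at or below half the pretreatment mean appears in 46 to 53% of patients as planned, and in 4 to 9% with matched windows.

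**Entry selection.** Protocol 6.1, criterion 3, requires a 7-day average of at least 0.5 at Visits 2 and 6, with a sponsor-judged exception.

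- In simulation A, keeping only patients who meet the score at Visit 6 moves the mean change to −0.06 to −0.07 under either method.
- In simulation B, keeping only those who meet it at both visits gives an apparent decrease in 62 to 75% as planned and 57 to 64% with matched windows.

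**The case against.** A reader might infer that the planned method is biased towards improvement. The documents do not support that. The error runs both ways, its mean under no effect is about zero before entry selection, and SAP 6.8.1 summarizes the mean change. The excess of apparent decreases comes from skew and vanishes when flares fill half of all days. After entry selection, most of the false improvement is regression to the mean, which matched windows leave in place. This part of the objection stands in full.

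A reader might also infer that one week at Week 20 decides the only natural-history comparison. It does not:

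- There is no test and no success criterion.
- Changes are reported at every visit and plotted by patient.
- The proportion of days is compared over matched 12-week periods. SAP Table JAJE.4 includes symptom-specific scores among its thresholds.
- The physician's global assessment and the retrospective records are further within-patient comparisons.

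The disease model is assumed. No section gives flare length, frequency or between-flare scores. A quiet-day score of 0.2 is close to the remission level of <0.15 cited in Protocol 3.2.5, while Protocol 3.2 also describes persistent features. In two of the four rows of simulation A, most visit weeks are not flare-free. A smaller gap between flare and quiet scores shrinks the absolute noise in proportion. In a two-state model without daily noise, it does not change the SD ratio.

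Finally, the Protocol states this endpoint at Week 20 and at various time points. Replacing the by-visit value by a period mean would change the question, so that step is not justified. None of this removes the window mismatch for the mean and symptom scores.

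**Conclusion.** The point holds as a matter of precision: a cheap improvement. For the mean daily diary score and the symptom scores, the plan compares a 7-day mean with a nominal 84-day mean when a matching on-treatment window is available. Over the flare patterns tried, the SD of the individual no-effect change is about 1.7 to 2.5 times that of a matched comparison. Under the assumptions of simulation B, before entry selection, a spurious halving appears in about half of untreated patients rather than under 10%. These sizes rest on assumed flare patterns. That the two windows differ follows from the text alone. The primary endpoint, change from Visit 6, is not affected.

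**What to change.** In SAP 6.8.3.1, add one row per NNS/CANDLE patient, overall and by symptom: the mean of all daily scores from after Visit 9 to Visit 12 (Week 8 to 20) minus the mean of all daily pretreatment scores. Show it alongside the by-visit 7-day changes, not in their place. In SAP 6.1.1, state the end day of the pretreatment window for patients who skip Visit 5, since the present text ends the window at a visit that they do not have.

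The cost is SAP wording and one derived variable from diary data already collected. The Protocol fixes no on-treatment averaging window for this change, so a supplementary row appears to need no amendment.

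Three downsides should be stated with the result:

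- The period mean describes average status over Week 8 to 20, not status at Week 20.
- SAP Section 3 shows that the primary-period and 52-week locks came before Version 5. If added now, the row must be labelled as introduced after those locks.
- It does not remove regression to the mean from the entry score of at least 0.5.

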## 6.2. Handling of Dropouts or Missing Data

If the year of birth is collected but the day and month are missing then July 1st will be used as the imputed month and day for purposes of age calculation.

For continuous measure, observed case analyses will be performed. In addition, a last observation carried forward (LOCF) imputation replaces missing data with the most recent non-missing post-baseline assessment for the endpoint of primary treatment period and maintenance treatment period.

## 6.3. Use of an “Efficacy Subset” of Patients

**Entered population** set includes those patients who sign the informed consent form directly or through their legally acceptable representatives.

**Enrolled population** set includes all patients who have entered the study and who are not considered screen fails at or before Visit 6 (i.e. patients not excluded due to not meeting inclusion criteria or meeting exclusion criteria during screening/pre-treatment period).

**Efficacy population** set includes all enrolled patients who have at least one dose of baricitinib.

**Safety population** set includes all enrolled patients who receive at least 1 dose of baricitinib and who did not discontinue the study for the reason “Lost to Follow-up” at the first postbaseline visit (Visit 7).

## 6.4. Patient Disposition

For enrolled population, a by-patient listing of the patient disposition (discontinued or completed) including the visit that occurred will be created. The listing will include the following information; patient ID, disease diagnosis, visit, disposition category (complete or the primary reasons for study discontinuation).

Frequency counts and percentages of patients who complete or discontinue early from the study will be summarized separately by disease diagnosis along with their reason for study discontinuation.

## 6.5. Patient Characteristics

A summary and list of demographic information and baseline characteristics of all enrolled patients will be created by disease diagnosis. The following continuous demographic and baseline characteristic variables will be summarized using descriptive statistics.

- Age at the time of study entry (in years).
- Height (cm)

- Weight (kg) (as recorded at Visit 6, unless missing, in which case the Visit 1 result will be used).

The following categorical variables will be summarized using frequency counts and percentages:

- Sex
- Weight categories (kg) (<10,  $\geq 10$  - <20,  $\geq 20$  - <30,  $\geq 30$  - <40,  $\geq 40$  - <50,  $\geq 50$  - <60, and  $\geq 60$ )
- Race
- estimated glomerular filtration rate (eGFR; mL/min/1.73 m^2)

A by-patient listing of demographic and baseline characteristics will be provided including age at study entry (years), body weight (kg), height (cm) and eGFR (mL/min/1.73 m^2). A by-patient listing of medical history and pre-existing conditions will be created.

## 6.6. Treatment Compliance

Treatment compliance was planned to calculate from treatment dispense and returned information from electronic CRF in the statistical analysis plan version 2. However, since these data were not collected at every visit, it was not possible to calculate the compliance by visit or treatment period. So treatment compliance will not be calculated.

Regarding the protocol deviation of treatment compliance, the information will be reported via monitoring.

## 6.7. Concomitant Therapy

Medications will be classified into anatomical therapeutic chemical (ATC) drug classes using the latest version of the World Health Organization (WHO) drug dictionary. Medication start and stop dates will be compared to the date of the first dose of study treatment (recorded on the Study Drug Administration page of the electronic case [clinical] report form [eCRF]) to allow medications to be classified as 'prior' or 'concomitant'. Medications that start and end before the first dose date will be classified as 'prior' medications. Medications that end on or after the first dose date will be classified as 'concomitant' medications. Note that medications with partial or missing start and/or stop dates will be assumed to be 'concomitant' unless there is evidence, through comparison of partial dates, to suggest otherwise. Concomitant medications will be summarized by disease diagnosis.

A by-patient listing of all non-steroid concomitant medications and steroid concomitant medications will be provided.

The total daily corticosteroid dose (mg), corticosteroid dose per weight (mg/kg), change from baseline, and percent change from baseline of corticosteroid doses will be listed.

## 6.8. Efficacy Analyses

### 6.8.1. Primary Outcome and Methodology

The primary objective is to determine if the administration of baricitinib to patients with NNS/CANDLE, SAVI, or AGS results in reduction in the patient's mean daily diary scores compared to baseline.

For change from baseline in patient's mean daily diary scores (defined in Section 6.9.1), descriptive statistics will be calculated by visit for NNS/CANDLE, SAVI, and AGS for baricitinib treatment period including dose adjustment period, primary treatment period and maintenance treatment period. Primary interest is to assess the mean change from baseline in patient's mean daily diary scores at Week 20 in NNS/CANDLE and Week32 in SAVI and AGS during primary treatment period, which is the primary endpoint of the study.

### 6.8.2. Additional Analyses of the Primary Outcome

Percentage of the patients who result in reduction in the patient's mean daily diary scores will be summarized by visit. [Table JAJE.3](#) shows a threshold of reduction in patient's mean daily diary scores. Additional threshold may be added.

**Table JAJE.3 Thresholds of reduction in patient's mean daily diary scores**

Variables	Disease	Threshold
Mean daily diary score	NNS/CANDLE	mean daily score to <0.5
	SAVI	mean daily score to <1.0
		mean daily score excluding the respiratory/breathing symptom score to <1.0
		mean daily score to <0.5
		mean daily score excluding the respiratory/breathing symptom score to <0.5
	AGS	mean daily score to <0.5
		mean daily score excluding neurological symptoms to <0.5

